#### **Medical History [paper source]**

- This section contains information regarding the participant's medical history, including exclusionary medical and psychiatric conditions.
- If any symptoms are endorsed on the Medical History in Section 8, the CRC will follow up with the participant asking:
  - How often and when was the last time you experienced these symptoms?
  - Do you ever take medication for this? If so, how often?
- Notes on the Medical History follow-up will be recorded at the bottom of the last page of the form to be reviewed by the study team.

#### **Demographics [direct EDC, sent 24 hrs before online screening visit]**

- This section contains information regarding the participant's gender, age, ethnicity, race, and education

#### **Use/History/Dependence [direct EDC, sent 24 hrs before online screening visit]**

- This section contains information regarding participant's use of nicotine replacement therapy, tobacco and e-cigarette product use, and drug/alcohol use
- Embedded in this section are the following standardized questionnaires: Nicotine Dependence Syndrome Scale, Fagerstrom Test for Cigarette Dependence, Penn State Electronic Cigarette Dependence Index

The steps for administering and reviewing questionnaires are found in the "Administering Forms and Questionnaires SOP."

The following will occur during the **in-person visit**:

### **6.2.3 Consent Documents**

The participant will be asked to sign the consent form (for an original copy to

give to the hospital) and two HIPPA forms (one for the Investigator and one for the hospital). These must be on source.

The HIPPA form must have “entire medical record” checked off in Section B and the optional activities of banking samples checked off & initialed in Section G. Participant will be presented with the Experimental Subjects Bill of Rights.

The e-consent form will be saved on the study server and held by the study team. The signed consent form will be given to 5B and kept at the CTSI.

#### **6.2.4 Urine Collection**

Approximately 150 mL of urine will be collected for a drug toxicology and pregnancy test (females only). If positive for illicit drugs without a valid prescription, the participant will be dismissed without payment. If positive for pregnancy, the participant will be dismissed and paid for the visit. The “Urine Toxicology Screen SOP” and “Pregnancy Screen SOP” are references for these testing processes.

#### **6.2.5 Physiological Measures**

The following physiological measures will be assessed:

- Height and Weight
- Blood pressure and heart rate

Out-of-range blood pressure and heart rates will be re-tested once via manual methods at the end of the visit. If still out of range, the participant will be deemed ineligible.

Steps for these assessments are found in the “Measuring Basic Vitals SOP.”

#### **6.2.6 Saliva Collection**

Participants will provide approximately 20mL of saliva for cotinine analysis. The steps for the saliva collection are found in the “Saliva Collection SOP.”

#### **6.2.7 NicAlert**

A NicAlert will be run in cases when the research team cannot wait for saliva cotinine results to come back from the lab. In this case, the NicAlert will serve as the primary cotinine eligibility criteria. Before running, these procedures should be checked by the project manager.

#### **6.2.8 End of Screening Visit**

At the end of the in-person screening visit, the participant will be asked to fill out a “Certificate of Participation” in order to receive compensation for the screening visit. The participant will be given a urine sample cup to take home. If eligible, they will provide a urine sample in this cup and bring in on the day of their orientation.

The participant will be dismissed and the CRC will inform them that they will be contacted in 1 week with eligibility results from the screening visit.

The participant's urine will be discarded and the CRC will store the participant's saliva in the freezer at the UCSF Tobacco Research Center lab. The saliva samples will be labeled with the Study ID and transferred to the [name] Lab at the end of the day on Wednesday afternoons. The CRC will complete a Screening Log on the Shared Lab Drive filling in information on the samples dropped off. Cotinine results will be expected the following Monday.

Participant Screening and Enrollment Log Passcode: [REDACTED]

### 6.3 ORIENTATION

After eligibility is determined, an Orientation visit will be conducted via Zoom. The orientation visit should be at least 24 hours before the first 5B study day. For example, if a participant was oriented on Monday at 12 noon, they should be booked to begin 5B visit on Wednesday morning. This is to ensure they have at least 1 full day to try the JUUL product.

At the remote orientation visit, the following will occur:

- The CRC will review with the participant 5B location, procedures and reminders to not use combusted marijuana and to not smoke from 10PM the night before their 5B admission
- Participants will watch a training video on JUUL
- Participants will be given two flavors to choose from (menthol and tobacco)
- Participants will collect approximately 150 mL of urine. This will be done at home right after the Zoom visit is complete. This will serve as Baseline total nicotine equivalents as a measure of usual daily intake of nicotine.
- Participants will conduct a “curb-side pick-up/drop off” their urine to be aliquoted into two 20mL vials; one vial pH adjusted.
- They will be given their own JUUL device and selected pods (1-2) to use for one whole day before the 5B admission. This will be done within the same day as the Zoom visit, the day before their 5B admission.
- If CTSI CRS is available during the orientation, participant and CRC will go to 5B for nurses to conduct a quick vein check. This is for the nurses to inspect the participant's veins and ensure a successful access the morning of the study.
- Participants will be randomized, using a Latin square design, to distinguish which ARM the participant will start off first for Hospital Study Day 1.

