#### 3.4.1 Inclusion Criteria

- Healthy on the basis of medical history and limited physical examination, as described below:
  - Heart rate < 105 BPM\*
  - Systolic Blood Pressure < 160 and > 90\*
  - Diastolic Blood Pressure < 100 and > 50\*
- \**Considered out of range if both machine and manual readings are above/below these thresholds.*
- Age:  $\geq 21$  &  $\leq 70$  years old
- Body Mass Index  $\leq 38.0$  (*at PI's discretion for higher BMI if no other concurrent health issues*)
- Willingness to avoid combusted marijuana up to 48 hours before each study visit
- Willingness to the avoid use of any non-legally sourced cannabis product for the duration of the study
- Nicotine strength of e-liquid of usual e-cigarette  $> 0$  mg/ml
- **Group 1 Experienced E-cigarette users**
  - Current use of tobacco cigarettes ( $< 5$  cigarettes per day)
  - Current e-cigarette use at least 15 days out of the past 30 days of a non-mod e-cigarette
- **Group 2 Primary Tobacco cigarette users:**
  - Currently smoking  $\geq 5$  cigarettes per day
  - Current e-cigarette use must be  $< 5$  times per month
- Saliva cotinine  $\geq 50$  ng/ml or urine cotinine and/or NicAlert=6
- Must have a smart phone, computer, or tablet and internet access (for remote procedures)

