**The below describes procedures if Hospital Study Day 1 assignment was the JUUL e-cigarette.**

### Pre PK – Baseline Assessments

- At 8 AM, the participant will be admitted to the research ward
- First morning urine void will occur at 8 AM and participant will be hydrated
- Breakfast will be served between 8:30-9:00 AM
- Expired CO will be measured to ensure the participant did not smoke any tobacco cigarettes
  - If the expired CO is  $\leq$ 5ppm, the participant will receive a \$50 cash bonus
  - If the expired CO is  $>$ 5ppm, the CRC must notify the PI (or co-I's) immediately. A decision on how to proceed will be based on PI discretion.
- At about 9 AM, an intravenous catheter will be placed in the forearm for blood sampling
- **Baseline questionnaires** will be collected after IV placement: MNWS, QSU ("no cig")
- CRC will weigh the JUUL e-cigarette with the pod in the device pre-vaping
- At approximately 9:15 AM, a blood sample will be collected for **baseline plasma nicotine**
- At approximately 9:15 AM, a blood sample will be collected for **baseline plasma catecholamines**
- At approximately 9:15 AM, a urine sample will be collected for **baseline total nicotine equivalents and VOC measurements**
- At approximately 9:15 AM, a heart rate and blood pressure will be measured 10 minutes before vaping session
- At approximately 9:24, a heart rate and blood pressure will be measured 1 minute before vaping session

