### Standardized JUUL Vaping Session (9:25:30 AM – 12 PM)

- At 9:25:30 AM, participants will vape the JUUL e-cigarette: ***one 3.5-second puff every 30-seconds for a total of 10 puffs.***

- **Questionnaires** administered during the standardized session: Henningfield Drug Liking Assessment
- **Skin blood flow** will be measured by laser Doppler Velocimetry. The probe will be placed on the right foot. Measurements will be taken 10 minutes before the standardized session, 5 minutes after the last puff, and 30 minutes after the last puff.

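### The overnight restriction and the CO check address smoking only, and the pre-session plasma nicotine that would measure carried-in vaping nicotine has no rule attached to it

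*Protocol*

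**What the plan says.** **Instruction.** Protocol 6.3 (Orientation) has the coordinator give "reminders to not use combusted marijuana and to not smoke from 10PM the night before their 5B admission". Vaping, the JUUL and nicotine are not named. The same list adds: "They will be given their own JUUL device and selected pods (1-2) to use for one whole day before the 5B admission". It sets no time by which use must stop, and nothing in the text calls the device back before Study Day 2.

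**Check at admission.** Protocol 6.5, Pre PK – Baseline Assessments: "Expired CO will be measured to ensure the participant did not smoke any tobacco cigarettes". The $50 bonus and the call to the PI both depend on the 5 ppm CO limit. If the limit is exceeded, "A decision on how to proceed will be based on PI discretion". The tobacco-day text (6.6) lists only its differences from the JUUL day and adds no check for vaping.

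**Timing.** "At 8 AM, the participant will be admitted to the research ward"; plasma nicotine is drawn at about 9:15; then "At 9:25:30 AM, participants will vape the JUUL e-cigarette". The tobacco session starts at the same clock time.

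**Population.** Group 1, planned as 15 of the 30, must show "Current e-cigarette use at least 15 days out of the past 30 days" (3.4.1).

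**Analysis.** For Aim 1 the SAP's Data Analysis Plan compares peak, time to peak and AUC in a crossover mixed model and forms AUC ratios, which it interprets as relative nicotine doses. It mentions no baseline subtraction and no baseline covariate, and it assigns no use to the 9:15 value.

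**The concern.** The overnight interval is what brings plasma nicotine down before the standardized session. If the restriction reaches cigarettes only, a participant can follow it, pass the CO check, collect the bonus and still arrive with nicotine from an e-cigarette. Half the planned sample are regular vapers, and everyone has a JUUL in hand before Day 1.

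The 9:15 sample would show this once assayed, but no rule responds to it. In an uncorrected analysis the carried-in nicotine is added to the session's peak and AUC and read as dose from the product under test. Pairing within participants does not remove the effect on a ratio: the same amount added to numerator and denominator pulls the ratio toward 1.

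**Working it through.** **The plan's own figure.** The documents give no figure for carry-in. The nearest is the SAP's 80% power for a ratio of 1.25 with 15 participants. With a mean of 200 ng/ml and a CV of 25%, the difference is 50 and the SD of a within-person difference is √2 × 50 = 70.7. The normal approximation is Φ(50/70.7 × √15 − 1.96) = Φ(0.779) = 78.2%, close to the stated value. That statement concerns daily exposure and is based on cotinine; the present point does not rest on it.

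**Inputs from the documents.** No smoking from 10 PM; admission at 8 AM; session at 9:25:30; sampling to 118 minutes after the session ends.

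**Assumed inputs, not in the documents.** Nicotine half-life of 1, 2 or 3 hours with simple exponential decline; residuals of 25% or 50% of the tobacco-session AUC; a true JUUL-to-tobacco AUC ratio of 0.80.

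**Step 1: share remaining at the session.** Share = 2^(−t / half-life), with t about 85 minutes from 8 AM and about 11.42 hours from 10 PM.

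| Half-life | Last use at 8 AM | Last use at 10 PM |
|---|---|---|
| 1 h | 37% | 0.04% |
| 2 h | 61% | 1.9% |
| 3 h | 72% | 7.2% |

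A faster early distribution phase would lower the 8 AM column.

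**Step 2: AUC added per 1 ng/ml at session start.** With k = ln 2 / half-life in minutes, the addition is (1 − e^(−118k)) / k. This gives 64, 86 and 95 ng·min/ml for 60, 120 and 180 minutes. It ignores the roughly 5 minutes of puffing before the 118-minute window opens.

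**Step 3: effect on the ratio.** Let r be the residual as a share of the tobacco-session AUC.
- Equal on both days: (0.80 + r)/(1 + r). For r = 0.25, 1.05/1.25 = 0.84. For r = 0.50, 1.30/1.50 = 0.87.
- Tied to one study day, whichever product is used: with sequences balanced, each product carries on average half of it. For r = 0.25, the ratio of mean AUCs is (0.80 + 0.125)/(1 + 0.125) = 0.82.
- Tied to one product's day: for r = 0.25, 0.80 + 0.25 = 1.05 if only JUUL days are affected, and 0.80/1.25 = 0.64 if only tobacco days are.

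Steps 2 and 3 cannot be joined. Turning ng/ml into a percentage needs a tobacco-session AUC, and the documents give none.

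**The case against.** **Carry-in is measured.** A reader might infer that vaping would go undetected altogether. It would not. Plasma nicotine and urine total nicotine equivalents are collected before the session under both conditions. What stands is narrower: the admission check would miss it, and no rule uses the later result.

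**The word smoke may be loose.** A reader might infer that participants are free to vape until 8 AM. The text does not say so. The Background calls users of both products smokers, and 6.5 houses JUUL sessions in a smoking room, so the reminder could be meant to cover both. Elsewhere, however, the protocol separates the two: Design Summary 3.1 contrasts smoking with vaping, and the exclusion on plans to quit names each. The ambiguity needs resolving, and the CO check cannot resolve it.

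**Other materials may be clearer.** The reminders summarise what the coordinator says. The consent form, phone script, slides, training video and SOPs were not available and may carry a wider instruction. This limits the claim to the reviewed text.

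**Reversal of the ratio.** The 1.05 result might suggest that the comparison could flip. It needs a residual that follows the assigned product, and the documents give no reason to expect one. The allocation table has 15 of each sequence in its first 30 rows, so a residual tied to Day 1 or Day 2 falls about equally on both products. The table is there to balance order, however, and does not make residuals equal or remove the pull toward 1.

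**Correction is not ruled out.** The SAP is silent on it, so every figure above is conditional on uncorrected values being analysed. That is what the plan as written describes.

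**Conclusion.** The point holds for the documents as reviewed. The overnight instruction and the compliance check address smoking; nothing restricts vaping before admission; and the one measurement that would reveal carry-in has no stated use. If the plan is followed literally, uncorrected carry-in counts toward Cmax and AUC in Aim 1.

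The size cannot be derived from the documents. On the assumed half-lives, the wording decides whether 37–72% or 0.04–7% of the nicotine from last use is still present at the session. On the assumed residuals, equal carry-in moves 0.80 to 0.84 or 0.87; unequal carry-in could move it either way. The documents do not support a claim that the bias is known to be large, that it favours one product, or that it reverses the result. Because the baseline sample is already drawn, the problem is largely repairable in the analysis.

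**What to change.** 1. **Protocol 6.3 and 6.5.** Reconcile the instruction and the admission check, so that the overnight restriction states that it covers e-cigarettes and the supplied JUUL as well as cigarettes, and so that CO is described as verifying the cigarette part only.
2. **SAP, Aim 1.** Pre-specify baseline-corrected Cmax and AUC using each day's 9:15 AM plasma nicotine C₀. For AUC, subtract C₀ × (1 − e^(−118k))/k, with the source of k stated; for Cmax, subtract the baseline decayed to the time of the peak. Entering C₀ as a period-specific covariate in the crossover model is an alternative.
3. **Sensitivity.** Report uncorrected values alongside. Do not exclude sessions from the main analysis for a high baseline: the documents offer no basis for a limit, and with about 15 per group each excluded session costs a crossover pair, possibly more often among vapers.

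**Cost.** A few words in the orientation text and one analysis paragraph; no new sample. Vapers may face slightly more overnight deprivation. The subtraction depends on an assumed decay: between half-lives of 1 and 3 hours it ranges from 64 to 95 ng·min/ml per 1 ng/ml, so results should be shown across that range.

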**Latin square design:**

Participant #	Sequence	Period 1	Period 2
1	A	JUUL	Tobacco
2	B	Tobacco	JUUL
3	A	JUUL	Tobacco
4	A	JUUL	Tobacco
5	B	Tobacco	JUUL
6	B	Tobacco	JUUL
7	B	Tobacco	JUUL
8	A	JUUL	Tobacco
9	A	JUUL	Tobacco
10	B	Tobacco	JUUL
11	A	JUUL	Tobacco
12	A	JUUL	Tobacco
13	B	Tobacco	JUUL
14	A	JUUL	Tobacco
15	B	Tobacco	JUUL
16	B	Tobacco	JUUL
17	A	JUUL	Tobacco
18	A	JUUL	Tobacco
19	B	Tobacco	JUUL
20	A	JUUL	Tobacco
21	B	Tobacco	JUUL
22	B	Tobacco	JUUL

23	A	JUUL	Tobacco
24	B	Tobacco	JUUL
25	A	JUUL	Tobacco
26	A	JUUL	Tobacco
27	B	Tobacco	JUUL
28	B	Tobacco	JUUL
29	A	JUUL	Tobacco
30	B	Tobacco	JUUL
31	B	Tobacco	JUUL
32	A	JUUL	Tobacco
33	B	Tobacco	JUUL
34	A	JUUL	Tobacco
35	B	Tobacco	JUUL
36	A	JUUL	Tobacco
37	B	Tobacco	JUUL
38	A	JUUL	Tobacco
39	B	Tobacco	JUUL
40	A	JUUL	Tobacco

#### 6.4 RT-PCR COVID-19 Testing Requirement

CTSI COVID-19 protocols will be followed.. If the participant has a positive result, they will not be able to participate at that time. Current guidelines typically include remaining in self-quarantine or seeking further care with a provider, should symptoms appear or worsen. We will ask that participants re-test no earlier than 14 days after the initial confirmed positive result. If the re-test is confirmed negative, we will allow that subject to participate in the study.

## 6.5 HOSPITAL STUDY DAY 1

Participants will be admitted to the hospital research ward the morning of their study visit at approximately 8am. Participants will be in a hospital-approved smoking room with negative pressure and a fan ventilating to the outside.

**The below describes procedures if Hospital Study Day 1 assignment was the JUUL e-cigarette.**

### Pre PK – Baseline Assessments

- At 8 AM, the participant will be admitted to the research ward
- First morning urine void will occur at 8 AM and participant will be hydrated
- Breakfast will be served between 8:30-9:00 AM
- Expired CO will be measured to ensure the participant did not smoke any tobacco cigarettes
  - If the expired CO is  $\leq$ 5ppm, the participant will receive a \$50 cash bonus
  - If the expired CO is  $>$ 5ppm, the CRC must notify the PI (or co-I's) immediately. A decision on how to proceed will be based on PI discretion.
- At about 9 AM, an intravenous catheter will be placed in the forearm for blood sampling
- **Baseline questionnaires** will be collected after IV placement: MNWS, QSU ("no cig")
- CRC will weigh the JUUL e-cigarette with the pod in the device pre-vaping
- At approximately 9:15 AM, a blood sample will be collected for **baseline plasma nicotine**
- At approximately 9:15 AM, a blood sample will be collected for **baseline plasma catecholamines**
- At approximately 9:15 AM, a urine sample will be collected for **baseline total nicotine equivalents and VOC measurements**
- At approximately 9:15 AM, a heart rate and blood pressure will be measured 10 minutes before vaping session
- At approximately 9:24, a heart rate and blood pressure will be measured 1 minute before vaping session

### Standardized JUUL Vaping Session (9:25:30 AM – 12 PM)

- At 9:25:30 AM, participants will vape the JUUL e-cigarette: ***one 3.5-second puff every 30-seconds for a total of 10 puffs.***

- **Questionnaires** administered during the standardized session: Henningfield Drug Liking Assessment
- **Skin blood flow** will be measured by laser Doppler Velocimetry. The probe will be placed on the right foot. Measurements will be taken 10 minutes before the standardized session, 5 minutes after the last puff, and 30 minutes after the last puff.

### PK Collection

- The CRC will weigh the JUUL after the puffing protocol is complete
- Blood samples will be collected at 2, 5, 7, 10, 15, 30, 60, 90, 118 minutes post end vaping session for **plasma nicotine**
- **Heart rate** will be collected at 2, 5, 7, 10, 15, 30, 45, 60, 75, 90, 100, 118 minutes post end vaping session
- **Blood pressure** will be collected at 5, 10, 15, 30, 45, 60, 75, 90, 100, 118 minutes post end vaping session
- Blood sample will be collected at 5 minutes post end vaping session for **plasma catecholamines**
- Urine Sample will be collected at 118 minutes post end of vaping session
- **Questionnaires** administered at **5, 10, 15, 30, 45, 60, and 120 minutes** post end vaping session: Henningfield Drug Liking Assessment; **5 minutes** post end vaping session: MNWS, QSU, mCES; **118 minutes** post end vaping session: MNWS, QSU("no cig")
- Lunch will be served around 11:30 AM, following the 118 min blood draw

### Ad Lib Use (12 PM – 4 PM)

- At approximately 12:00 PM , a 4 hour ad lib video taped session will begin and participants will be allowed to use the JUUL as they wish
- CRC will weigh the JUUL e-cigarette before ad lib begins
- **Questionnaires** administered half-way through ad lib at approximately **1:30PM**: MNWS, QSU, mCES; **5, 10, 15, 30, 45, 60, and 120 minutes** post ad lib start: Henningfield Drug Liking Assessment
- Blood samples will be collected every 30 minutes during ad lib at 12:30 PM, 1:00 PM, 1:30 PM, 2:00 PM, 2:30 PM, 3:00 PM, 3:30 PM & 4:00 PM for **plasma nicotine**
- Urine Sample will be collected at 195 minutes into Ad Lib session
- **Final questionnaires** administered at 3:50 PM: MNWS, QSU, mCES, Overall Drug Liking Assessment, GRPQ for JUUL, Utility of E-Cigs Questionnaire
- CRC obtains final weight of JUUL e-cigarette
- At 4:00pm the participant is discharged from the hospital ward

## 6.6 HOSPITAL STUDY DAY 2

In most cases, hospital study day 2 will occur directly after study day 1, however if it is more convenient for the participant to reschedule to a later time, they can complete study day 2 between 2 days and up to one week from study day 1. **The below describes procedures if Hospital Study Day 1 assignment was the JUUL vaping.**

The tobacco cigarette ARM will differ from the JUUL e-cigarette ARM in the following ways:

### Pre PK – Baseline Assessments

- CRC will weigh the tobacco cigarette before smoking

### Standardized Smoking Session

- At 9:25:30 AM, participants will smoke their usual tobacco cigarette: ***one 3.5-second puff every 30-seconds for a total of 10 puffs.***
- **Questionnaires** administered during the standardized session: Henningfield Drug Liking Assessment

